The potential participant will be notified by the PI or RA if she qualifies for the study or does not meet the criteria for the study. If a new mother qualifies for the study, the PI or RA will briefly describe the study and time commitment. The PI or RA will explain the study's purpose and procedures and read the consent form to all potential participants. After the potential participant's questions are addressed and verbal consent to participate is obtained, the new mother will sign the informed consent form. If the new mother agrees to participate, an appointment will be scheduled at the participants' next scheduled clinic visit or at the current time and location with the PI or RA to complete Visit 1. Participants may also choose to complete study visits 1-3 during their current visit or at another designated location with the PI.

E(3). Incentives. If applicable, provide the amount, type, and time of distribution of any payment/incentive to participants.

All participants have the opportunity to receive a total of \$100.00 to compensate for their time:

Visit 1: \$40.00

Visit 2: \$20.00

Visit 3: \$40.00

Identification of Participants; Data Collection and Storage; Equipment; Records Retention

A. Identification of Participants. Indicate whether the data collected may contain individual identifiers (need for "confidentiality"), or whether the data will be collected anonymously.

Confidential

B. Data Collection. Describe the method(s) or procedure(s) for data collection **in step-by-step, layman's terms** (include collecting party, frequency, duration, location, etc).

The use of audio or video recording must be justified by the research purpose/objective or future research.

Participants will complete a daily 60 minute CES treatment and meet with the PI for three visits three weeks apart for a total of six weeks. Each visit will take approximately 60-80 minutes to complete.

• **Visit 1/First day of treatment**

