During study Visit 1 the PI or RA will explain the study and answer any questions. Participants will complete a urine pregnancy test. If the urine pregnancy test is negative baseline measures using the HAM-A14, HAM-D17, PSQI19, ISI7, and BIMF20 questionnaires will be completed by the participant with researcher assistance. Participants will then be given an Alpha-Stim® AID CES device kit with a serial number. The PI or RA will instruct participants on how to use the Alpha-Stim® AID CES device; then the participant will be asked to complete a 60-minute treatment. After the completion of the treatment, the participant will be asked about any side-effects or problems the participant may have experienced. Any side-effects information will be recorded on a side-effect form using the subject's words that describe what happened. The protocol for study treatments at home will be explained to you, and any questions will be answered. The participant will be reminded to complete your daily 60 minute CES treatment before the Visit 2 meeting. The participant will receive a \$40.00 Target Gift Card after Visit 1.

• **Visit 2**

At study Visit 2 The participant will be asked to complete a urine pregnancy test. If the urine pregnancy test is negative the participant will be asked to complete the HAM-A14, HAM-D17, PSQI19, ISI7, and BIMF20 questionnaires with researcher assistance. Your log will be reviewed and discussed. The participant will be asked about any side-effects that the participant may have experienced. The protocol for study treatments at home will be reviewed and the following device supplies will be given to you: six new AAA batteries and two 15ml. bottle conducting solution. The process of how to contact the PI or RA will be reviewed. The participant will be reminded to complete your daily 60 minute CES treatment before the Visit 3 meeting. The participant will receive a \$20.00 Target Gift Card after Visit 2.

• **Visit 3/ Last day of treatment**

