At study Visit 3 The participant will be asked to complete a urine pregnancy test. If the urine pregnancy test is negative the participant will be asked to complete the HAM-A14, HAM-D17, PSQI19, ISI7, and BIMF20 questionnaires with PI or RA assistance. The subject's log will be reviewed and discussed as needed. The participant will be asked about any side-effects that the participant may have experienced. The Alpha-Stim® AID CES device and all supplies will be returned to the study team. The participant will receive a \$40.00 Target Gift Card after Visit 3.

C. Equipment. Describe any equipment to be used (e.g., audio, visual), ownership (e.g., TAMUCC, personal), and methods of storage (e.g., password, location).

Study Device: The Alpha-Stim® AID will be used for this study (Figure 1). The Alpha-Stim® AID is a prescriptive device and is FDA cleared for the treatment of anxiety, insomnia, and depression. About the size of a smart phone, the Alpha-Stim AID emits a mild electrical current via ear clip electrodes. The technical specifications for the Alpha-Stim® AID are shown on pages, 15-16. One-half of the devices will be active CES devices (0.5 Hz, 100 μ A (subsensory level), 50% duty cycle, biphasic asymmetrical rectangular waves) using ear clip electrodes. The other one-half of the devices (sham CES) will be identical to the active CES device except the ear clip electrodes will not emit electricity. The FDA has approved the device to be down classified from Class III to Class II (Federal Register, 2014). Subjects will complete a daily one hour CES treatment using ear clip electrodes (Figure 2.) with current set at fixed level of 100 μ A (subsensory level) for active CES treatment group for 6 weeks. The procedure will be the same for the sham group, but the Alpha-Stim® AID ear clips will not emit electricity.

Findings to date indicate that the Alpha-Stim® AID is an effective treatment with broad applications for a variety of syndromes for the management of anxiety, depression, and insomnia, or for the short-term relief of the symptoms of anxiety, depression and/or insomnia. In many cases it is the sole therapeutic method required.

Treatment Regimen:

The treatment regimen is one daily 60 minutes Alpha-Stim® CES treatment using ear clip electrodes for 6 weeks at 0.5 Hz, 50% duty cycle with a fixed current of 100 μ A (subsensory level). The sham CES unit is identical except the sham ear clip electrodes do not emit electricity.

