Method for Assigning Subjects to Treatment Groups:

The blocked randomization method will be used to assign participants to active and sham groups (Efid, 2011). Participants will be assigned to CES treatment or sham CES using a 1:1 ratio. Electromedical Products International, Inc. (EPI) will randomize the assignment of appropriate devices to active or sham groups by using a random list of computer generated numbers (1 for active and 2 for sham) in randomly selected block sizes. An EPI device log will be developed as follows: The appropriate device, either active or sham will be assigned to a subject's number in the study (1 – 10, etc.), starting with number 1, in sequential order and the device's serial number will be listed on the EPI device log in the far-right column, Device Serial Number. The EPI log will remain in the EPI office. EPI will enter all device serial numbers on the Investigator device log in the order they are listed on the EPI device log. Study personnel will assign a device to a participant by using the next available device serial number in the order it is listed on the investigator device log. If a participant drops out of the study, that subject's device will be used for the replacement subject. If for some reason, the participant does not return the device, EPI will be notified and they will send the appropriate device, either active or sham, for the replacement subject. The device box will contain an equal number of active and sham CES device kits. The devices will be packed by EPI in the device box in the order of the device serial numbers on the device log. Only EPI has a list of numbers of the devices assigned to the active and sham groups. The PI, RA and participants are blinded to which participants have Alpha-Stim® CES active or sham devices until data analysis is complete. After the last participant completes the study and all data are entered, an individual completely independent of the study and data analysis, for example a database manager, will assign de-identified participants to unidentified groups using the serial numbers provided by EPI. After the completion of data analysis, blinding will be broken.

D. Data Storage. Describe how the data collected will be stored, location(s), how the confidentiality of individually identifiable information will be maintained (if applicable), and who will have access. (For audio and video recordings, include transcripts).

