B. Mechanism of Protection. Describe **every potential risk** to human subjects that may result from participation in the research ("Risk"), and indicate the method or procedure to be used to mitigate the potential risk ("Protection Mechanism"). Consider physical, psychological, social, legal, and economic risks (*e.g., breach of confidentiality, injury, psychological distress, pressure to conform, pressure to participate, etc.*).

	Risk	Protection Mechanism
1.	Breach of confidentiality	Confidentiality will be maintained for the participants by assigning their names as numbers during questionnaire administration and by assigning numbers to the treatment log.
2.	Severe levels of anxiety or depression are identified	The PI or RA, who is an experienced clinicians, will make referrals to the appropriate resources and healthcare provider.
3.	Side-effects: Side-effects seen in approximately 4,541 patients in controlled, open, uncontrolled conditions, and by physician survey and reasonably associated with the use of CES are dizziness (6 cases, 0.13%), skin irritation/electrode burns (5 cases, 0.11%), and headaches (9 cases, 0.20%). Prolonged CES treatment at higher than necessary currents may cause dizziness or nausea that can last from hours to days.	Side-effects are usually mild and self-limiting. Adverse effects are generally seen with treatment at higher than necessary currents. For this study, the active CES unit will be preset by the manufacturer and cannot be independently manipulated. Therefore, higher currents cannot occur. The sham CES unit will be inactive and the ear clip electrodes will not emit electricity. If side effects occur during the use of CES participants will be referred back to their OB/GYN.
4.	As with any therapeutic intervention, not all participants in the treatment group will respond to the Alpha-Stim® AID. Participants randomly assigned to the SHAM group will not receive treatment.	PI or RA will discuss this possibility with participants during informed consent process.
5.		
6.		
7.		
8.		
9.		
10.		

C. Outside Assistance. If applicable, describe any outside assistance available to participants to mitigate the Risks stated above and how this information will be provided (e.g., medical care, counseling, etc).

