This study is not expected to involve psychological, social, physical, economic, academic, or legal risks of harm to participants or living children any greater than those ordinarily encountered in daily life. However, if a participant is identified to have severe levels of stress, anxiety, or depression the PI or RA, who is an experienced clinicians, will make referrals to the appropriate resources and health care provider. If side effects occur during the use of CES participants will be referred back to their OB/GYN.

Benefits to Participants; Benefits to Society

A. Benefits to Participants. If applicable, describe the potential benefits to participants as a result of taking part in the research (exclude payments/incentives). If there are no benefits, then state so.

Participants may benefit from this study by becoming more aware of their current mental health status and realizing perceptions about their own health and relationship to maternal functioning.

B. Benefits to Society. Describe the potential benefits to society or contribution to generalizable knowledge as a result of the research.

The information derived from this study can provide important information about the efficacy and adverse effects of a clinical interventions by controlling the variables that could impact the results of the study. It may also provide important information about maternal psychological distress that could translate to health care costs and use.

Waiver of Informed Consent; Informed Consent Process

A(1). Is a waiver of signed informed consent requested? (See Criteria for Waiver of Signed Informed Consent at the end of the HSRP for guidance).
 
If "no," go to B.
	
Y 
	
N 
	
A(2). If "yes," select which criteria applies, then go to B. (See Criteria for Waiver of Signed Informed Consent at the end of the HSRP for guidance).
	
---	-----------------------------------	--	---	--

B. Informed Consent Process. Describe **step-by-step** how informed consent will be obtained from participants (i.e., who, what, where, when, how).

- Note:
- 1) Participants must be given time to review the informed consent and supporting documents and ask questions.
 - 2) For **minor participants**, researchers must obtain both parental informed consent and a separate child assent written at an appropriate reading level.

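### A woman who stops the device early is replaced, and the protocol schedules no HAM-A14, side-effect question or reason for stopping after that point

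*Protocol*

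**What the plan says.** **Drop-out.** Under Method for Assigning Subjects to Treatment Groups the protocol says: "If a participant drops out of the study, that subject's device will be used for the replacement subject". Return of the device is presumed and non-return is the exception: "If for some reason, the participant does not return the device, EPI will be notified", after which the manufacturer sends a device of the same type for the replacement. No assessment, date, reason or side-effect question is attached to either sentence.

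**Staying in the study.** Inclusion criterion 9 makes completion of 85% of treatments, given as 36, a condition of continuing. Exclusion criterion 9 has a woman who becomes pregnant dropped at once, with follow-up mentioned but not described.

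**Assessments.** Under Data Collection, participants "meet with the PI for three visits three weeks apart for a total of six weeks". The visits run from "Visit 1/First day of treatment" to "Visit 3/ Last day of treatment". The HAM-A14 and the other scales appear at each of the three visits, after a negative pregnancy test. Side effects are asked about at the same three visits. At Visit 3, "The Alpha-Stim® AID CES device and all supplies will be returned to the study team".

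**Side effects.** Mechanism of Protection (row 3) and Outside Assistance both say: "If side effects occur during the use of CES participants will be referred back to their OB/GYN". Benefits to Society lists "important information about the efficacy and adverse effects of a clinical interventions" among what the study can provide.

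**The concern.** The protocol does not separate stopping the device from leaving the study. A woman who stops early cannot meet the treatment count, so the text gives a site no basis for seeing her at week 6. It tells the site to pass her device to someone else. Her replacement restores the number of women but not the comparison that randomisation set up, because the woman replaced was also randomised.

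Stopping may be related to outcome. It can follow lack of benefit in either arm, or a side effect. If so, the six-week HAM-A14 contrast compares women who persisted with the device in one arm with women who persisted in the other. Without a reason for stopping or a later score, nobody could judge afterwards whether the losses were harmless. The account of side effects likewise lacks whatever happened between the last attended visit and the exit.

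**Working it through.** **1. Does stopping the device lead to leaving the study?** Daily treatment for 6 weeks is 6 × 7 = 42 sessions. Then 0.85 × 42 = 35.7, which rounds up to the protocol's 36. A woman who stops at any time in the first five weeks has at most 5 × 7 = 35 sessions, below 36. One who stops at the end of week 4 has at most 28. Read with inclusion criterion 9, almost any early stop ends participation.

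**2. What is on record for her?**

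| Stops between | HAM-A14 held | Side effects asked about | At exit |
|---|---|---|---|
| Visit 1 and Visit 2 | Baseline only | After the first session | Nothing scheduled |
| Visit 2 and Visit 3 | Baseline and week 3 | Up to week 3 | Nothing scheduled |

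In neither row is there a week-6 score.

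**3. How many women?** The protocol's own figure reproduces: 44 / (1 − 0.10) = 48.9, and 44 × 1.10 = 48.4. Both round up to 49, and the target is set at 50. At 10% attrition, 0.10 × 50 = 5 women have no final score. If drop-outs are replaced until 50 complete, 50 / 0.90 = 55.6 are randomised and about 5.6 have no final score. If attrition were 5% or 20% instead (assumed range), 50 / 0.95 − 50 = 2.6 or 50 / 0.80 − 50 = 12.5 would have none.

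**4. What could this do to the HAM-A14 difference?** Let p be the share lost in an arm and g the number of points by which those lost would have scored worse at week 6 than completers in that arm. A completers-only difference favours active too much by

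bias = p(active) × g(active) − p(sham) × g(sham).

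With the same g in both arms this is [p(active) − p(sham)] × g. The protocol gives neither the split nor g, so both are assumptions. I take g as 3 to 6 points and 25 women per arm.

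- Equal shares, equal g: bias = 0.
- 3 active, 2 sham: (3/25 − 2/25) × 3 to 6 = 0.04 × 3 to 6 = 0.12 to 0.24 points.
- 4 active, 1 sham: (4/25 − 1/25) × 3 to 6 = 0.12 × 3 to 6 = 0.36 to 0.72 points in favour of active.
- 1 active, 4 sham: the same size, against active.
- Equal shares of 10%, but g = 6 in active and 3 in sham: 0.10 × 6 − 0.10 × 3 = 0.30 points.

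**5. Side effects.** Mechanism of Protection cites 6 + 5 + 9 = 20 cases in about 4,541 patients. That is 20 / 4,541 = 0.44%, or 25 × 0.0044 = 0.11 expected cases in an active arm of 25.

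**The case against.** The strongest reply is that this is an omission: nothing forbids an exit assessment. The consent pages, the side-effect form and the treatment log are not in the text at hand, and a withdrawal procedure or a reason field could sit there. The drop-out sentence is about leaving the study, not about stopping the device, and the only condition stated for the questionnaires at Visits 2 and 3 is a negative pregnancy test. The protocol states no completers-only analysis, and the analysis plan is not shown.

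Part of this stands. One cannot say that reasons or events will certainly go unrecorded, only that the protocol text schedules no step to record them. Someone has to hear of a side effect in order to refer the woman, and Visit 2 includes a review of how to reach the study team. But the treatment-count rule links stopping the device to leaving, and an analysis plan can only choose how to handle missing scores.

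Three stronger readings are tempting and are not supported.

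- A reader might infer that Visit 3 is defined in two conflicting ways, by week and by end of treatment. The regimen and the visit schedule both span six weeks, so the wording in the heading is a schedule label that mirrors the one for Visit 1. Nothing instructs a site to move Visit 3 to an early stop.
- A reader might infer that a sizeable side-effect rate would vanish from the record. The protocol's cited 0.44% points to few such cases. The firmer ground is the missing HAM-A14 and the missing reason for stopping.
- A reader might infer that the result will be biased towards active CES. No document supports a one-sided split, and loss from the sham arm for lack of benefit would push the other way.

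**Conclusion.** The point holds as a gap that the stated rules make worse. Replacing drop-outs, together with the 36-treatment condition, leaves early stoppers without any HAM-A14 after they stop, and the text provides no exit record. The size is uncertain. About 5 of 50 women would be affected at the protocol's own attrition rate, and the bias is nil with balanced losses and equal gaps. The 0.36 to 0.72 points rest on the assumed 4-to-1 split, the assumed gap of 3 to 6 points and an analysis of completers. The attrition allowance covers the lost numbers but not this bias. Because the loss cannot be repaired later and the remedy is small, the protocol should be changed.

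**What to change.** Amend Data Collection and Method for Assigning Subjects to Treatment Groups as follows.

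1. State that a woman who stops using the device stays in the study unless she withdraws consent. She is asked to complete the existing questionnaires and side-effect form at the remaining scheduled visits, at weeks 3 and 6 counted from Visit 1. A replacement may still be enrolled, but the first woman's data are kept.
2. If she will attend no further visit, record the date of and reason for stopping and any side effects since the last visit. Where possible, also take a HAM-A14, dated and labelled as an early score rather than as Visit 3. This can be done when the device is returned or by a call, since the protocol does not say how a drop-out's device comes back.
3. Reconcile these steps with inclusion criterion 9 (36 treatments), with exclusion criterion 9 (pregnancy) and with the negative-test condition on the questionnaires, so that none of them by itself ends outcome collection. Without this the amendment would contradict those rules. It sets no rule on when treatment stops.
4. Add a few words making clear that the end-of-treatment wording in the Visit 3 heading is a label for the week-6 visit.

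The cost is a short amendment and a few extra contacts for about 5 women, using existing forms. The downside is that scores taken off treatment enter the comparison and may slightly dilute the observed effect.
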